5.2.2 Exclusion Phase 1b

1. Active central nervous system involvement by autoimmune disease (e.g., neuropsychiatric SLE including seizures, psychosis, acute confusional state or cerebrovascular accident) requiring specific therapeutic intervention within 60 days prior to first day of study treatment. Headache treated only with acetaminophen, NSAIDs, or approved doses of triptans is permitted with medical monitor approval.
2. Presence of another rheumatic (overlap) disease that may confound clinical assessments in the study. Secondary sicca or Sjogren's syndrome, antiphospholipid antibody syndrome, and overlap with RA without erosive joint disease ("rhupus") are allowed.
3. History of antiphospholipid syndrome with thromboembolic event within 12 months of screening or not on an adequate anticoagulation regimen. However, presence of antiphospholipid antibodies alone (without a history of thromboembolic event) is not exclusionary.
4. Receipt of any of the following treatments within the following timeframes before screening (see [Section 14.5](#), Appendix E, for excluded medications):
 - a) Systemic corticosteroids \geq 100 mg prednisone or equivalent: 4 weeks
 - b) Intra-articular therapies, such as corticosteroids or hyaluronic acid preparations: 4 weeks
 - c) Intravenous immunoglobulin (IVIg): 4 weeks
 - d) Other non-biologic immunosuppressive agents, such as cyclosporine and tacrolimus: 4 weeks
 - e) Cyclophosphamide: 12 weeks

-
- f) Cytokine antagonists, including but not limited to interleukin (IL)-1, IL-6, IL-17, IL-12/23, IL-23, interferon (IFN), integrin, and tumor necrosis factor (TNF)- α antagonists: 12 weeks
 - g) B-cell-depleting therapies (e.g., rituximab): 24 weeks with levels of circulating cluster of differentiation 19+ (CD19+) B cells within normal limits or 48 weeks if CD19+ count is not available
 - h) Belimumab, abatacept, or atacicept: 12 weeks
 - i) Other biologics or investigational drugs: 8 weeks or 5 half-lives, whichever is longer
 - j) Transfusion with blood, packed red blood cells, platelets or treatment with plasmapheresis or plasma exchange: 6 weeks
5. Patient has had recent serious or ongoing infection, or risk for serious infection, including:
- a) Acute or chronic infections:
 - Requiring systemic antibiotic, antifungal, or antiviral (antimicrobial) therapy within 14 days of Week 1, Day 1
 - Requiring hospitalization or a course of IV antimicrobial therapy within 24 weeks prior to screening
 - b) History of severe and/or disseminated viral infections, and/or opportunistic infections
 - c) Known seropositivity for or active infection by human immunodeficiency virus (HIV)
 - d) Active, chronic, or resolved hepatitis B or hepatitis C infection (see [Section 8.2.6.6](#))
 - e) History of progressive multifocal leukoencephalopathy
 - f) Active or latent tuberculosis (TB), as suggested by chest x-ray within the 12 weeks prior to screening and/or QuantiFERON[®]-TB Gold at screening per [Section 8.2.6.6](#)
 - Patients with a history of latent TB with documented completed treatment per Centers for Disease Control and Prevention guidelines are allowed
 - A chest x-ray must be performed during screening if one has not been done within 12 weeks prior to the screening visit
 - g) Receipt of a live-attenuated vaccine within 12 weeks of first day of study treatment (Week 1, Day 1)
 - h) Primary immunodeficiency (unless otherwise considered, in the opinion of the investigator and medical monitor, to confer a clinically insignificant infection risk, such as deficiency in immunoglobulin A (IgA), C1q, C2, or C4 without a history of recurrent infections [3 or more infections in 1 year requiring antimicrobial therapy])
6. History of any concurrent illness, including drug induced SLE, that has required treatment with oral or parenteral corticosteroids for more than a total of 2 weeks within the last 24 weeks prior to signing the ICF
-

-
7. Clinical evidence of significant unstable or uncontrolled acute or chronic diseases (e.g., cardiac [including congestive heart failure, hypertension, angina, or history of myocardial infarction], pulmonary [including chronic obstructive pulmonary disease, asthma requiring corticosteroid therapy, pulmonary hypertension, or pulmonary fibrosis], hematologic, gastrointestinal, hepatic, renal, neurological, or infectious diseases) that, in the opinion of the investigator or sponsor, could confound the results of the study, put the patient at undue risk, or interfere with protocol adherence
 8. History of cancer, except for in situ cancer that has been completely excised or has been curatively treated with no sign of disease for > 5 years
 9. Major surgery within 4 weeks before signing the ICF or major surgery planned during the study period

5.2.3 Inclusion Phase 2

1. Male or female patients aged 18 to 75 years (inclusive)
 2. BMI of ≥ 18 kg/m²
 3. Fulfills the 2012 SLICC classification criteria for SLE
 4. At least one of the following at Screening per central lab:
 - a) Positive ANA test (1:80 or higher) or
 - b) Anti-dsDNA antibodies elevated to above normal (i.e., positive results); or
 - c) Anti-Smith antibody at screening elevated to above normal (i.e., positive results)
 5. Active nephritis with UPCR ≥ 1.0 measured in 24-hour urine collection
 6. Currently receiving one or more immunosuppressive agents (see [Section 7.2](#) for allowed background medications and [Section 14.5](#), Appendix E for excluded medications) that has been stable for dose and route of administration for ≥ 8 weeks prior to Baseline. If patient is also on corticosteroids then must be on a stable dose for ≥ 2 weeks prior to Baseline
 7. Renal biopsy within 2 years of the Screening visit with a histologic diagnosis of LN (ISN/RPS) Classes III, IV-S or IV-G, (A) or (A/C) +/- Class V; for biopsies > 1 year before the Screening visit, one of the following must also be present at screening: low C3, low C4, or anti-ds-DNA elevated to above normal range.
 8. Acceptable screening laboratory values:
 - a) Adequate hematologic criteria:
 - Absolute neutrophil count $\geq 1.5 \times 10^9/L$ ($\geq 1 \times 10^9/L$ if neutropenia is attributable to lupus disease activity)
 - White blood cells $\geq 2.0 \times 10^9/L$ ($\geq 1.5 \times 10^9/L$ if leukopenia is attributable to lupus disease activity)
 - Absolute lymphocyte count $\geq 0.5 \times 10^9/L$
 - Hgb ≥ 9 g/dL (≥ 8 g/dL if anemia is attributable to lupus disease activity)
-

-
- Platelet count $\geq 100 \times 10^9/L$ ($\geq 25 \times 10^9/L$ if thrombocytopenia is attributable to lupus disease activity)
- b) Adequate hepatic function:
- Total bilirubin $\leq 1.5 \times ULN$ ($3 \times ULN$ for patients with known Gilbert's syndrome)
 - AST $\leq 2.5 \times ULN$
 - ALT $\leq 2.5 \times ULN$
- c) eGFR ≥ 30 mL/min/1.73 m² estimated based on CKD-EPI formula
- d) IgG ≥ 500 mg/dL
9. Female patients of childbearing potential must have a negative serum pregnancy test at Screening and a negative urine pregnancy test at Baseline and must agree to employ adequate birth control measures for the duration of the study. Women of childbearing potential (WOCBP) must use highly effective and medically acceptable methods of contraception to prevent pregnancy during Screening and must agree to continue to practice adequate contraception during the study and for 4 weeks after administration of the last dose of the study drug.

For the purposes of this study, WOCBP are defined as: all postpubescent female patients, unless the patient is postmenopausal (defined by amenorrhea for at least 2 years or amenorrhea for at least 1 year with confirmatory follicle stimulating hormone [FSH] level in the postmenopausal range as documented historically or measured by the central laboratory at Screening and if patient is not on supplementary hormonal therapy) or if the patient is surgically sterile (i.e., tubal ligation, hysterectomy, bilateral salpingoophorectomy).

Highly effective contraception is defined as the use of an intrauterine device or hormonal contraceptives (e.g., implant or oral), or having a vasectomized partner. If using a hormonal form of contraception, it must have been stable for at least 4 weeks prior to Screening, and if using concomitant mycophenolate, the patient must use another nonhormonal form of highly effective contraception. Abstinence will be acceptable only if it is in line with the preferred and usual lifestyle of the patient. Periodic abstinence (e.g., calendar, ovulation) and withdrawal are not acceptable methods of contraception.

10. Male patients with a partner of childbearing potential must be either congenitally sterile or surgically sterile (by vasectomy) or willing to use a condom in addition to having their female partner use another form of contraception (such as an intrauterine device, barrier method with spermicide, or hormonal contraceptive [e.g., implant, injectable, patch, or oral]) from Screening until 12 weeks after the last dose of study drug, unless their partners are infertile or surgically sterile.
11. Willing and able to provide written informed consent prior to any study-related procedures and to comply with all study requirements

5.2.4 Exclusion Phase 2

1. Any of the following:
 - a) Dialysis within 12 months prior to Screening or expected need for renal replacement therapy (dialysis or renal transplant) within a 6-month period after enrollment
 - b) Rapidly progressive glomerulonephritis (RPGN) and/or renal disease other than ISN/RPS Classes III, IV-S or IV-G, [A] or [A/C] with or without Class V LN)
 - c) Chronic kidney disease not due to LN
 - d) > 50% sclerosed glomeruli on most recent renal biopsy
 2. Presence of another rheumatic (overlap) disease that may confound clinical assessments in the study. Secondary sicca or Sjogren's syndrome and antiphospholipid antibody syndrome are allowed
 3. History of antiphospholipid syndrome with history of thromboembolic event within 12 months of screening
 4. Active central nervous system involvement by autoimmune disease (e.g., neuropsychiatric SLE including seizures, psychosis, acute confusional state or cerebrovascular accident) requiring specific therapeutic intervention within 60 days prior to first day of study treatment. Headache treated only with acetaminophen, NSAIDs, or approved doses of triptans is permitted with medical monitor approval.
 5. Active or chronic infection:
 - a) Acute or chronic bacterial or fungal infections:
 - Requiring systemic antibiotic or antifungal therapy within 14 days of Screening
 - Receipt of more than a 14-day course of antimicrobial therapy within 12 weeks of Screening to treat sepsis, abscess, osteomyelitis, joint infection, or bacterial endocarditis.
 - b) Acute viral illness:
 - Signs and symptoms of acute viral illness must be resolved \geq 4 weeks prior to Day 1 (Baseline). Patients with history of SARS-CoV-2 must have full resolution of symptoms and no evidence of associated renal injury
 - Symptomatic herpes zoster or herpes simplex infection (HSV) (not including simple oral HSV lesions) within 12 weeks prior to Screening or during the Screening Period
 - Acute hepatitis B or C infection
 - c) Chronic viral infection:
 - Patients with chronic herpesvirus infections such as HSV or CMV should be on suppressive therapy at Baseline and during the study
 - Chronic hepatitis C infection. Patients with prior chronic hepatitis C infection should have received a full treatment course and have documented absence of detectable HCV DNA at the completion of at least 12 weeks of treatment
-

-
- Chronic hepatitis B infection. Patients who are HBsAg negative and hepatitis B core antibody positive with no detectable DNA will be allowed into the study and will require regular monitoring of hepatitis B virus DNA (see [Section 8.2.6.6](#)).
 - Known seropositivity for or active infection with human immunodeficiency virus (HIV). Those with a positive screening test and negative confirmatory test are eligible.
6. Patient has or had any of the following:
 - a) Progressive multifocal leukoencephalopathy
 - b) Active or untreated latent TB, per QuantiFERON-TB Gold at screening per [Section 8.2.6.6](#)
 - Patients with a history of latent TB with documented completed treatment per Centers for Disease Control and Prevention guidelines are allowed
 - A chest x-ray must be performed during screening if one has not been done within 12 weeks prior to the screening visit
 - c) Receipt of a live-attenuated vaccine within 12 weeks of Baseline (Week 1, Day 1)
 - d) Primary immunodeficiency (unless otherwise considered, in the opinion of the investigator and medical monitor, to confer a clinically insignificant infection risk, such as deficiency in IgA, C1q, C2, or C4 without a history of recurrent infections [3 or more infections in 1 year requiring antimicrobial therapy])
 - e) Primary hematopoietic cell or solid organ transplant
 7. Clinical evidence of significant unstable or uncontrolled acute or chronic diseases (e.g., cardiac [including congestive heart failure, hypertension, angina, or history of myocardial infarction], pulmonary [including chronic obstructive pulmonary disease, asthma requiring corticosteroid therapy, pulmonary hypertension, or pulmonary fibrosis], hematologic, gastrointestinal, hepatic, renal, neurological, or infectious diseases) that, in the opinion of the investigator or sponsor, could confound the results of the study, put the patient at undue risk, or interfere with protocol adherence
 8. QT interval with Fridericia's correction (QTcF) or Bazett's correction (QTcB) > 480 msec on ECG
 9. Major surgery within 12 weeks before signing the ICF or major surgery planned during the study period
 10. Any active or suspected malignancy or history of documented malignancy within the last 5 years before Screening. Exceptions include history of appropriately excised and cured cervical carcinoma in situ or excised basal or squamous cell carcinomas of the skin
 11. Women who are pregnant or lactating
 12. Hypersensitivity to the Investigational Medicinal Products or any of its excipients.
 13. Use of investigation medical therapy or device, and/or participation in an investigational trial < 8 weeks or 5 half-lives, whichever is longer, prior to Baseline; Patients who participated in Phase 1b of KZR-616-002 are excluded from Phase 2
-

6 STUDY DRUG

6.1 KZR-616

6.1.1 Physical Description

KZR-616 is a small molecule, covalent inhibitor of the immunoproteasome. Two subcutaneous formulations, described below, have been manufactured for clinical use and formulated as the maleate salt of KZR-616.

1. KZR-616 Maleate SC Injection: A frozen solution drug product that is supplied in vials containing 150 mg/mL KZR-616 (180 mg/mL KZR-616 maleate) in a vehicle of [REDACTED]. This drug product is shipped on dry ice (-70°C) and stored at -17.5° ± 7.5° C
2. KZR-616 Lyophile: A lyophilized drug product that is supplied in vials containing 125-mg KZR-616 (150-mg KZR-616 maleate) and [REDACTED] (inactive excipient) per vial. Each vial is reconstituted with sterile water for injection (WFI) prior to administration. This drug product is shipped on dry ice (-70° C) and stored at 2° to 8°C.

6.1.2 Packaging and Labeling

The frozen solution drug product will be supplied in single-use vials packaged in multi-vial cartons.

The lyophilized drug product will be supplied in single-use vials packaged in multi-vial cartons.

All investigational products will be labeled according to appropriate regulatory guidelines.

All packaging and labeling operations will be performed according to Good Manufacturing Practice (GMP) for Medicinal Products and the relevant regulatory requirements.

6.1.3 Storage of KZR-616

Refer to the Investigator's Brochure and Pharmacy Manual for storage conditions for KZR-616.

The investigator or designee must confirm appropriate temperature conditions have been maintained during transit for all investigational product received and any discrepancies are reported and resolved before use of the investigational drug product.

Only participants enrolled in the study may receive investigational product and only authorized site staff may supply or administer investigational product. All investigational products should be stored in an environmentally controlled and monitored (manual or automated) area in accordance with the labeled storage conditions. Access to investigational product must be limited to the investigator and authorized site staff.

The investigator, institution, or the head of the medical institution (where applicable) is responsible for study treatment accountability, reconciliation, and record maintenance (such as receipt, reconciliation and final disposition records).

6.2 Study Drug Accountability

On receipt of the study drug, the investigator (or deputy) will conduct an inventory of the supplies and verify that study drug supplies are received intact and in the correct amounts. The monitor may check the study supplies at each study center at any time during the study.

It is the responsibility of the study monitor to ensure that the investigator (or deputy) has correctly documented the amount of the study drug received, dispensed, and returned on the dispensing log that will be provided. A full drug accountability log will be maintained at the study center at all times. The study monitor will perform an inventory of study drug at the closeout visit to the study center. All discrepancies must be accounted for and documented.

7 DOSAGE AND TREATMENT ADMINISTRATION

7.1 KZR-616 Treatment Administration

For both the Phase 1b and the Phase 2 portions of the study, KZR-616 will be administered as a SC injection once weekly for 13 and 24 doses, respectively. Further details regarding drug product formulation, preparation and administration of KZR-616 will be provided in a separate Pharmacy Manual/Investigational Product Handling Manual.

Phase 1b:

At least 6 patients per dose level will be enrolled sequentially to receive SC injection of KZR-616 at 45 mg, 60 mg, and 75 mg, respectively. For dose levels ≥ 60 mg, patients should receive at least one prior dose of 30 mg (i.e., Step-up dosing).

Phase 2:

Patients in the Phase 2 portion will receive KZR-616, 60 mg. Dose administration will include a Week 1 dose of 30 mg followed by an increase to 60 mg (i.e., Step-up dosing) for Week 2-Week 24 unless dose is reduced.

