 - If 0 or 1 of 6, 0 or 1 of 5, or 0 of 4 patients (20% or less) in a cohort experience a DLT, the next dose level will be opened for enrollment
 - If 1 of 4 (25%) of patients in a cohort, or 2 or more of 5 or 6 patients in a cohort experience a DLT, the maximum tolerated dose will have been exceeded and dose escalation will not continue

If dose escalation is halted due to excessive DLTs, dose escalation may resume if a review by the DMC of all cumulative data identifies a possible mitigating intervention(s) (e.g., corticosteroid pre-medication for injection site reaction). In such an instance, dose escalation may resume by enrolling at least 4 new patients in a new cohort at the same dose level at which escalation ceased, implementing the proposed intervention, and following the dose escalation guidelines above. If successful, any subsequent dose levels must incorporate the new intervention.

Dose escalation will occur after safety data for at least 4 patients, who received KZR-616 for at least 4 weeks, are reviewed and evaluated by the DMC.

Patients who discontinue treatment prior to Week 5 will be considered DLT non-evaluable, unless they experience a DLT prior to Week 5. The DLT non-evaluable patients may be replaced until the necessary number of evaluable patients is achieved per dose level.

Dose escalation increments other than 15 mg may be proposed by the DMC based upon emerging safety, PK, PD, and/or efficacy data. Similarly, emerging data may prompt the DMC to recommend a different safety evaluation period, or alteration of the dosing interval or duration.

[figure not shown]
Phase 1b will be completed upon fulfillment of enrollment of the highest dose level that is determined to be tolerated.

Phase 2:

Eligible patients with active proliferative LN who are treated with at least one immunosuppressive agent will receive KZR-616, 60 mg, weekly for 24 weeks.

Patients will be followed for 12 weeks after the last dose of study drug.

Study schematic for Phase 1b and Phase 2:

Abbreviations: DLT = dose limiting toxicity; SLE = Systemic Lupus Erythematosus

Treatment:

KZR-616 is a small molecule, covalent inhibitor of the immunoproteasome.

KZR-616 is supplied as both a frozen solution drug product and a refrigerated lyophilized drug product in single-use vials packaged in multi-vial cartons.

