4.1.1.2 Dose Escalation Plan

For each dose level, at least 6 patients may be enrolled to assure the availability of at least 4 DLT-evaluable patients. Dose escalation guidelines are as follows:

- Each cohort within a dose level will include 1 sentinel patient who will receive KZR-616 at a selected dose on Day 1/Week 1
- If the sentinel patient does not experience a DLT, as defined below, within 48 hours and based on the clinical judgement of the investigator and medical monitor, the remaining patients in the cohort will be dosed
- If a DLT is experienced in the sentinel patient within 48 hours of injection, a second sentinel patient may be dosed with KZR-616 following a safety review by the DMC. If no DLT is observed after 48 hours in the second sentinel patient, the remainder of the cohort may be enrolled
- If 0 or 1 of 6, 0 or 1 of 5, or 0 of 4 patients (20% or less) in a cohort experience a DLT, the next dose level will be opened for enrollment after DMC review as below
- If 1 of 4 (25%) patients in a cohort, or 2 or more of 5 or 6 patients in a cohort experience a DLT, the maximum tolerated dose will have been exceeded and dose escalation will not continue

To evaluate tolerability, a minimum of 4 patients should receive KZR-616 at a specified dose level for at least 4 weeks prior to any decision by the DMC to dose escalate.

Patients who discontinue treatment prior to Week 5 will be considered DLT non-evaluable, unless they experience a DLT prior to Week 5. The DLT non-evaluable patients may be replaced until the necessary number of evaluable patients is achieved per dose level.

Escalation is planned to continue in 15 mg increments of KZR-616. Planned dose levels of KZR-616 to be explored are described in [Table 2](#) below. Other dose escalation increments may be proposed by the DMC based upon emerging safety, PK, PD, and/or efficacy data. Similarly, emerging data may prompt the DMC to recommend a different DLT evaluation period, or alteration of the dosing interval or duration. During the dose escalation period, and based on safety evaluation in patients, the DMC may also recommend that patients in subsequent dose cohorts receive prophylactic treatment (e.g., pulse corticosteroid and/or antihistamine) prior to initial doses to prevent AEs and/or intra-patient dose escalation to be employed with an initial tolerizing dose of 30 mg.

Table 2: KZR-616 Dose Levels

Dose of KZR-616 (mg)
45 mg
60 mg
75 mg

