10.7 Data Monitoring Committee

To enhance the safety and integrity of the study data, a study-specific DMC consisting of principal investigators, medical monitors, and Kezar Life Sciences (hereafter, Kezar) designees will be convened to review the accumulating safety data for the study.

For Phase 1b, safety review will occur for each cohort as it completes the first 4 weeks of treatment. The first safety review by the DMC will occur after the first 6 patients have been enrolled and received study drug and progressed to Week 4. Decisions to escalate, expand, or modify dose level(s) or frequency will depend on review of safety data by the DMC.

The DMC will review cumulative Phase 1b study data and provide a recommendation for the Phase 2 dose.

For Phase 2, the DMC will convene and review cumulative data on a periodic basis to be defined in a separate DMC charter.

The specific responsibilities and composition of the DMC are outlined in a separate DMC Charter. In addition, the details of outputs provided for the meetings will be referenced in the separate document.

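### Phase 1b, 60 mg and above: with step-up, the 48-hour sentinel hold clears a 30 mg dose, and the Week 5 review falls one week short of 4 weeks at the cohort dose

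*Combined protocol and SAP*

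**What the plan says.** Section 7.1 sets the dosing for Phase 1b: "For dose levels ≥ 60 mg, patients should receive at least one prior dose of 30 mg (i.e., Step-up dosing". The number of 30 mg doses is left open. Appendix A has no run-in visit and starts dosing at Week 1, so any 30 mg dose falls within the 13 weekly doses.

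Section 4.1.1.2 treats step-up as something that the DMC may recommend for later cohorts: "intra-patient dose escalation to be employed with an initial tolerizing dose of 30 mg". The same section has two timing rules.

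- **Sentinel.** Each cohort has "1 sentinel patient who will receive KZR-616 at a selected dose on Day 1/Week 1". The rest of the cohort is released on this condition: "If the sentinel patient does not experience a DLT, as defined below, within 48 hours", together with the judgement of the investigator and medical monitor.
- **Escalation.** The rule is that "a minimum of 4 patients should receive KZR-616 at a specified dose level for at least 4 weeks prior to any decision" to escalate.

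A patient who stops treatment before Week 5 without a DLT is not evaluable. Appendix A places Week 5 on Day 29. Section 10.7 uses the same clock: "safety review will occur for each cohort as it completes the first 4 weeks of treatment". Section 4.1.1.1 gives a 4-week DLT period but no start day.

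**The concern.** A sentinel patient is useful only if that patient meets the exposure of interest before the others do. Section 2.5.1 says that systemic reactions are more likely with first doses of 60 mg or above, typically begin 8 to 24 hours after dosing, and usually resolve within 48 hours. A 48-hour hold suits that pattern, provided it follows the dose that carries the risk. Under step-up it follows a 30 mg dose, which is below even the 45 mg starting level. As background, Section 7.1.3 reports a systemic drug reaction in 4 of 12 healthy volunteers given 60 mg.

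The second issue concerns the escalation decision. If the DMC meets when the cohort completes 4 weeks of treatment, one of those weeks was spent at 30 mg. The DMC must then either breach the 4-weeks-at-level rule or wait a week that no section schedules.

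**Working it through.** **The plan's own thresholds.** Section 4.1.1.2 allows escalation at 20% or less and stops at 25%. These reproduce: 1/6 = 16.7%, 1/5 = 20.0%, 1/4 = 25.0%. The thresholds are not in question; the exposure behind them is.

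**Day count.** Inputs: weekly doses on Days 1, 8, 15 and 22, and Week 5 on Day 29 (Appendix A); the number of 30 mg doses, k, with k at least 1 under Section 7.1. Then:

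- first cohort-level dose = Day 1 + 7k
- cohort-level doses before Day 29 = 4 − k
- days at the cohort level by Day 29 = 29 − (1 + 7k) = 28 − 7k
- 28 days at the cohort level reached on Day 1 + 7k + 28 = Day 29 + 7k

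| k | First cohort-level dose | Doses before Day 29 | Days at level by Day 29 | 28 days at level reached |
|---|---|---|---|---|
| 0 | Day 1 | 4 | 28 | Day 29 |
| 1 | Day 8 | 3 | 21 | Day 36 |
| 2 | Day 15 | 2 | 14 | Day 43 |

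The Week 5 cut-off and the 4-weeks-at-level rule agree only when there is no step-up.

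**Sentinel timing, k = 1.** The written hold ends on Day 3. A hold after the first cohort-level dose would end on Day 8 + 2 = Day 10. If the next patient starts on sentinel Day 3, that patient's own Day 8 is sentinel Day 3 + 7 = Day 10. The nominal gap between the two first cohort-level doses is therefore 10 − 8 = 2 days. Appendix A allows ±1 day at that visit for each patient, so the gap can run from 2 − 2 = 0 to 2 + 2 = 4 days. Nothing in the rule prevents a gap shorter than 48 hours.

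**What a shorter window could do (illustration).** Assume an equal DLT hazard at each cohort-level dose and none at 30 mg. Let p be the true DLT probability over 4 cohort-level doses; the documents give no value, so take 0.1 to 0.4. Over 3 doses the probability is q = 1 − (1 − p)^0.75. With 6 evaluable patients, P(escalate) = (1 − q)^6 + 6q(1 − q)^5; with 4 evaluable patients it is (1 − q)^4. For 4 doses, p replaces q.

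| p | q (3 doses) | n = 6: 4 vs 3 doses | n = 4: 4 vs 3 doses |
|---|---|---|---|
| 0.1 | 0.076 | 0.886 vs 0.930 | 0.656 vs 0.729 |
| 0.2 | 0.154 | 0.655 vs 0.767 | 0.410 vs 0.512 |
| 0.3 | 0.235 | 0.420 vs 0.571 | 0.240 vs 0.343 |
| 0.4 | 0.318 | 0.233 vs 0.382 | 0.130 vs 0.216 |

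The rise in escalation probability is 0.04 to 0.15 with 6 patients and 0.07 to 0.10 with 4. If DLTs cluster at the first cohort-level dose, as Section 2.5.1 suggests for systemic reactions, the rise is smaller.

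**The case against.** Sections 7.1 and 4.1.1.2 can be read together: 7.1 sets the default at 60 mg and above, and 4.1.1.2 gives the DMC a wider power over any later cohort. A reader might infer a contradiction about whether step-up happens, but following 7.1 breaches nothing in 4.1.1.2. That objection stands.

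A reader might also infer that the DLT window misses the first cohort-level dose. It does not: with one 30 mg dose, Day 8 lies inside a window that starts on Day 1, so a qualifying reaction to it counts. The DMC may also change the window.

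Nor is the patient unprotected after Day 8. Section 7.1.1 sets criteria before every dose. Section 9.1 stops an individual's dosing for any event meeting DLT criteria, inside the window or not. Sections 7.1.3 and 10.5 require systemic injection reactions to be reported within 24 hours. Section 2.5.1 adds that single doses of up to 75 mg were well tolerated after a 30 mg start. All of this lowers the risk. None of it obliges the other patients to wait until the sentinel has been observed at the cohort dose, which is what a sentinel rule is for.

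The 4-week sentence could also be read as time assigned to a cohort, so that the 30 mg week counts. The conflict then disappears, but escalation would rest on 3 cohort-level doses, and the text should say so.

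**Conclusion.** The point holds as a gap in a safety rule, limited to Phase 1b levels of 60 mg and above. It affects no planned patients if escalation stops at 45 mg, at least 6 if only 60 mg opens, and at least 6 + 6 = 12 if 75 mg opens too. The sentinel hold is the more important part: as written it clears 30 mg, and the first 60 or 75 mg dose has no hold. The second part is a mismatch of one week (Day 29 against Day 36; 21 days against 28; 3 doses against 4). Both rest on a single step-up dose; more 30 mg doses widen the mismatch. The documents do not say whether cohorts at these levels remain to be dosed, and the DMC charter, which may add detail, is not available here.

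Three further inferences are not supported.

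- **Pooled adverse event tables.** A reader might infer that the tables will mix stepped and un-stepped patients, because the synopsis allows "enrolling at least 4 new patients in a new cohort at the same dose level at which escalation ceased" with a new mitigation. This needs both regimens to occur at one level and the dose/treatment groups not to separate them. Neither is stated.
- **Section 7.1.4.** Its bar on intra-patient escalation is most naturally read as limiting re-escalation after a reduction, not as forbidding step-up.
- **Synopsis and Phase 2.** The synopsis text omits step-up, which is clerical. Phase 2 is clear in Sections 4.1.2 and 7.1.

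**What to change.** In Sections 4.1.1.2 and 7.1:

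1. Make one 30 mg dose at Week 1 the default at 60 mg and above, counted within the 13. Wording it as a default leaves the DMC free to vary it.
2. Keep the Day 1 sentinel check. Add that no other patient in the cohort receives 60 or 75 mg until 48 hours have passed without a DLT after the sentinel's first cohort-level dose.
3. Start the DLT window on Day 1 and run it to 28 days after the first cohort-level dose (Day 36 with one step-up dose). Do not move the start to Day 8: a related Grade 3 event on Days 1 to 7 would then not count, although Section 2.5.3 expects DLTs mainly at first exposure.
4. Align the Week 5 evaluability rule and the review timing in Section 10.7 with that window.

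**Cost.** Each review at 60 mg and above moves about one week later. Day 36 is already a scheduled visit, so no visits are added, and the planned number of patients does not change. The window lengthens from 28 to 35 days at these levels, which is slightly stricter. A patient who stops between Day 29 and Day 36 without a DLT would become non-evaluable and could be replaced. The added hold is a minor scheduling constraint: a patient who starts on sentinel Day 3 and keeps to nominal visit days already meets it.
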